4.6 Patients' health status (CAT) (secondary objective #1)

Table 14. Patients' health status (CAT) at each study visit

The table will provide patient distribution by CAT questionnaire total score (as defined in "Computed variables" chapter, considering the following categories: < 10 / 10 - 20 / 21 - 30 / > 30) at each study visit.

The table will also provide the descriptive statistics (mean, median, standard deviation, quartiles, min, max) of CAT questionnaire total score (as defined in “Computed variables” chapter) at each study visit. Changes from enrollment in CAT total score (see ‘Computed variables’ chapter) will be also summarized by visit. 95% confidence intervals limits of the mean will be provided for each estimate.

Descriptives will be calculated over the number of patients respectively evaluable at the time point considered, namely at enrollment (i.e. FAS patients), at 6 months (i.e. evaluable patients at 6 months) and at 12 months (i.e. evaluable patients at 12 months).

(Missing values will be replaced according scoring algorithm as defined in “Computed variables” chapter, maximum two missing values are accepted).

4.7 Patients’ dyspnea (mMRC) (secondary objective #1)

Table 15. Patients’ dyspnea (mMRC) at each study visit

Absolute and relative frequency of the mMRC grade at each study visit [F15_MMRC.MMRC] (see Appendix 8.2); percentages will be calculated over the number of patients respectively evaluable at the time point considered, namely at enrollment (i.e. FAS patients), at 6 months (i.e. evaluable patients at 6 months) and at 12 months (i.e. evaluable patients at 12 months). 95% confidence intervals limits will be provided for each proportion.

4.8 Patients’ COPD awareness

Table 16. Patients’ COPD awareness (Awareness structured interview) each study visit

The table will provide:

- absolute and relative frequencies of patients’ answers to each the COPD awareness questionnaire item [F12_AWARENESS.AWARENESS_01 – AWARENESS_27] at each study visit;
- the descriptive statistics (mean, median, standard deviation, quartiles, min, max) of the COPD awareness questionnaire composite scores (see ‘Computed variables’ chapter) at each study visit.

Changes from enrollment in the COPD awareness composite scores (see ‘Computed variables’ chapter) will be also summarized by visit.

95% confidence intervals limits of the mean will be provided for each estimate.

Descriptives will be calculated over the number of patients respectively evaluable at the time point considered, namely at enrollment (i.e. FAS patients), at 6 months (i.e. evaluable patients at 6 months) and at 12 months (i.e. evaluable patients at 12 months).

4.9 **Relation between treatment satisfaction and demographic/clinical parameters and PROs during 12 month observation period (secondary objective #2)**

The purpose of this secondary analysis is not to obtain a predictive model, but to investigate the relationship among pre-defined variables and outcomes that are of clinical interest. In fact, the intent of this analysis is mainly exploratory and not confirmatory of any a priori hypotheses (consistently with the Study Protocol indications).

Among independent variables in the model, the PROs used in the study are symptomatic tools routinely used in clinical practice to evaluate disease activity and severity (i.e. mMRC and CAT) as per the patient's perspective. Patients' treatment satisfaction could also depend on their clinical status (that would be measured through the mMRC or the CAT) and on their adherence to treatment (MMAS-4 score). This is the reason why the PROs measures are taken into account in exploring the relationship between patient's treatment satisfaction and clinical status.

Contrary to what is stated in paragraph 9.7 of the Study Protocol, the Sponsor on the 12/09/2017 decided not to include the covariates post-baseline in this analysis: therefore, only data collected at enrollment visit will be considered in the mixed models for repeated measures described below, with the exception of the dependent variables (i.e. TSQM-9 scores, that will be considered at each timepoint).

Table 17. Relation between treatment satisfaction and demographic/clinical parameters and PROs during 12 month observation period (Repeated measures regression models) – Effectiveness domain

A regression model will be estimated; the dependent variable will be the effectiveness domain score of TSQM-9 and the independent ones will be the following:

- age and gender at enrollment;
- number of exacerbations at enrollment;
- relevant spirometry parameters at enrollment (a selection of the following parameter will be done, based on data availability: FEV1, FVC, FEV1 % of the predicted, RV, TLC, DLCO);
- patient's disease severity in terms of level of dyspnea (mMRC score) or CAT total score (depending on data availability) at enrollment (since they are expected to be intercorrelated measures, as reported by 2017 GOLD guidelines, only one of such measures will be considered in the model);
- MMAS-4 score at enrollment.

Center will be included as random effect and study visit (visit1/enrollment, visit2/6months, and visit3/12months) as timepoint.

During data elaboration, the Biostatistician will assess the intercorrelation between the proposed variables, in order to evaluate the opportunity to exclude some of the listed independent variables that are highly associated to each other; in case of important lack of data for certain parameters, such parameters may be excluded as well from the final model.

Because measures referred to the dependent variable will be collected at each study visit, a mixed model for repeated measures will be estimated; moreover, interaction terms between independent variables will be evaluated and, if not significant, they will not be included in the final model. The optimal covariance structure will be evaluated during analysis (preferably "first-order autoregressive correlation" or "unstructured" options). A stepwise selection method will be evaluated during the analysis in order to identify the variables to be included in the final model.

The patients switching treatment during observation period will not be excluded from analysis. The patients stopping treatment during study will be censored at last available visit.

The analysis will be performed considering only evaluable patients at 12 months.

Table 18. Relation between treatment satisfaction and demographic/clinical parameters and PROs during 12 month observation period (Repeated measures regression models) – Convenience domain

See previous model characteristics: in this analysis, the dependent variable will be the convenience domain score of TSQM-9.

Table 19. Relation between treatment satisfaction and demographic/clinical parameters and PROs during 12 month observation period (Repeated measures regression models) – Global satisfaction domain

See previous model characteristics: in this analysis, the dependent variable will be the global satisfaction domain score of TSQM-9.

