7. RATIONALE AND BACKGROUND

COPD is a debilitating disease characterized by poorly reversible airflow limitation, breathlessness on exertion (1-2), exercise intolerance (3) and limitations in the capacity to perform daily activities (4-5).

In studies that have explored patient perspectives regarding the burden and impact of COPD, predominant complaints are shortness of breath and limitations in the ability to participate in activities (6), which negatively impact on social interactions and result in loss of independence (7-8).

Patient satisfaction with their medication is shown to affect treatment-related behaviors, such as their likelihood of continuing to use their medication, to use their medication correctly and to adhere with medication regimen (9). Treatment satisfaction may give useful insights not only into the patients' perspective on their current treatment but also about differentiation among alternative treatments. Treatment satisfaction is defined as the individual's rating of important attributes of the process and outcomes of his/her treatment experience (11). It focuses on one aspect of satisfaction with medical care and involves the interaction of expectations, preferences, and satisfaction with medical treatment. Treatment satisfaction assessment is potentially useful for understanding the patient's perspective on their current treatment and can be helpful to differentiate among alternative treatments (14-15). Patient expectations, demographic characteristics, such as age and education, and personal preferences affect treatment satisfaction. The pattern and characteristics (that is, side effects and effectiveness) of ongoing treatments for COPD, and the duration/severity of COPD influence perceptions of treatment satisfaction. More important are the factors most directly connected to the treatment, and the way the treatment is delivered and directly experienced by the patient. Outcomes of treatment, including impact on symptoms and adherence with the treatment regimen, represent an important determinant of treatment satisfaction. In 2012 only the 14.3% of Italian patients affected by obstructive respiratory syndromes was adherent to treatment (48).

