| Eligibility criteria Inclusion and exclusion criteria, Informed consent and privacy form | X | | |
| Baseline information (Socio-)demographic variables: age, gender, race, geographic location, housing situation, marital status, educational and employment status | X | | |
| Weight, body mass index | X | X | X |
| Physical examination | X | X | X |
| Life Habits Smoking (yes/no, number of pack/years, smoke duration) | X | X | X |
| Medical History and concomitant diseases. - Charlson Comorbidity Index. | X | X | X |
| COPD medical history: Date of COPD diagnosis (years from diagnosis); n° of COPD exacerbations/year during the previous year to enrolment visit | X | | |
| Functional assessment Lung function test results (FEV1, FVC, FEV1 % of the predicted, RV, TLC,DLCO) according to clinical practice | X | X | X |
| CAT questionnaire | X | X | X |
| COPD Exacerbations** after enrollment Onset and resolution date Severity (mild, moderate, severe) | X | X | X |
| Disease severity (GOLD 2015 Guidelines) | X | X | X |
| Medications related to COPD, COPD exacerbations and adverse events (LABA, LAMA, SABA, SAMA, ICS/LABA, steroids, antibiotics, etc.): drug, dose, frequency, duration of therapy. - Long-Term Oxygen Therapy (liquid and/or concentrate). | X | X | X |
| Change of therapy during observation period and reason for change. | | X | X |
| Non Pharmacological treatment - Pulmonary rehabilitation- | X | X | X |
| Health-care resource consumption related to COPD, COPD | X | X | X |

| Study Visits | Visit 1 | Visit 2 | Visit 3 |
|--|----------|-----------------|-------------------|
| | Baseline | Follow-up | Follow-up 2 |
| Months | 0 | 6 (+/-1) | 12 (+/- 1) |
| exacerbations and adverse events: 
 • Drugs • hospitalization (inward and day hospital) • emergency room access • outpatient visits • GP visits • laboratory tests • clinical examinations | | | |
| Patient Reported Outcomes Questionnaires/scales | | | |
| TSQM-9 | X | X | X |
| MMRC (modified MRC dyspnea scale) | X | X | X |
| CAT | X | X | X |
| MMAS-4 (Morisky Medication-Taking Adherence Scale) | X | X | X |
| Brief Illness Perception Questionnaire | X | X | X |
| Awareness structured interview | X | X | X |
| S(AE) assessment | | X | X |

Table 1. Recorded variables.

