9.13 LIMITATIONS OF THE RESEARCH METHODS

This is a non-interventional (observational) study which puts patients under observation for one year prospectively. However information, selection and/or recall bias have to be taken into account, as in all non-interventional studies.

Investigators could select patients in order to enroll those ones who most probably will be followed up or most probably correctly understand the questionnaires (selection bias). In order to limit this bias, monitoring visits could be randomly performed in sites to verify whether enrolment was performed consecutively.

The information to be captured is usually recorded in medical charts or on questionnaires filled in during visit: this also should limit recall bias of information.

As regards confounding, the primary aim of the study is to evaluate the patients' satisfaction for medical treatment irrespective of the ongoing treatment, no causality nor associations to treatments will be evaluated because of the lack of a control group. The regression models to analyze the relation between treatment satisfaction scores and demographic, clinical and PROs parameters during a 12-month observation (secondary objective #2) will provide adjusted estimates of the impact on satisfaction scores of each variable keeping constant the others included in the models.

Patients with missing values will not be excluded from the analysis, their data will not be replaced; frequency of missing data will be given for all analyzed variables. Patients with missing and not missing values in TSQM9 domain scores will be described according to main socio-demographic and clinical features.

As far as generalizability of results, the study aims to provide information on COPD patients enrolled in the study; it does not mean to be generalized to the population of Italian COPD patients, because sites are selected. However sampling is based on consecutive enrolment, in order to avoid patient selection during recruitment.

Finally, target sample size is considered to be achievable during the enrolment period on the basis of preliminary feasibility considerations.

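### The objective #2 models leave out education and COPD duration, which the protocol names as determinants of satisfaction and collects at enrolment, so some of their coefficients may be confounded

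*SAP*

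**What the plan says.** Protocol section 7 makes two statements about what drives the outcome: "Patient expectations, demographic characteristics, such as age and education, and personal preferences affect treatment satisfaction", and "the duration/severity of COPD influence perceptions of treatment satisfaction".

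The schedule in Protocol 9.3, Table 1, has "educational and employment status" and the date of COPD diagnosis at Visit 1, and the "Charlson Comorbidity Index" at all three visits. SAP section 3 derives COPD duration in years from the diagnosis date. The SAP then describes education (Table 4), COPD duration (Table 6) and ongoing comorbidities (Table 7).

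The Table 17 model in SAP 4.9, reused for Tables 18 and 19, has these covariates: "age and gender at enrollment"; exacerbations recorded at enrolment; a selection of spirometry parameters; mMRC or CAT; and MMAS-4. Centre is a random effect and visit the time factor. Stepwise selection is left open. The covariate list in Protocol 9.7 likewise has no education, duration or comorbidity. Neither document gives a reason.

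Protocol 9.13, where it deals with confounding, says the models will give "adjusted estimates of the impact on satisfaction scores of each variable keeping constant the others included in the models".

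**The concern.** A determinant of the outcome that is left out of a regression can distort the coefficient of any included covariate it is associated with, given the other covariates. Here the protocol itself asserts that education and disease duration bear on satisfaction, and then points to models without them when it addresses confounding. Objective #2 gives its demographic and clinical parameters as examples only, so both variables are within its scope.

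At stake is how Tables 17-19 are read. A coefficient for exacerbations, dyspnoea or CAT, or adherence could partly reflect schooling or years since diagnosis. The SAP argues for its patient-reported covariates on the ground that satisfaction may depend on clinical status and adherence. Section 7 of the protocol makes a firmer claim for education and duration, so the same reasoning would admit them.

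**Working it through.** **1. Named, collected, modelled**

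| Variable | Named in Protocol 7 | Available at enrolment | In Tables 17-19 |
|---|---|---|---|
| Age | yes | yes | yes |
| Education | yes | yes (SAP Table 4) | no |
| COPD severity | yes | yes (spirometry, mMRC, CAT) | yes |
| COPD duration | yes | yes (derived, SAP Table 6) | no |
| Comorbidity | no | yes (SAP Table 7; Charlson only where ICD-9-CM codes exist, Protocol 9.4) | no |

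The gap among the named determinants in this table is education and duration. Severity, which the protocol pairs with duration, is represented.

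**2. The plan's own precision figures**

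Protocol 9.5, Table 2, uses SE = SD/√n and half-width = 1.96 × SE.
- SD 21.4: 21.4/√380 = 1.098, half-width 2.152; 21.4/√320 = 1.196, half-width 2.345.
- SD 16.6: 16.6/√380 = 0.852, half-width 1.669; 16.6/√320 = 0.928, half-width 1.819.

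All eight entries reproduce. They concern the mean score only; the documents give no precision figure for the regression models.

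**3. Possible size of the bias**

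For one omitted variable, on the standardised scale, bias = b × r. Here b is its effect on satisfaction given the included covariates, and r is its partial association with the covariate of interest. The documents give neither, so both are assumptions: b from 0 to 0.3 and r from 0 to 0.5. With n = 320 (the lower effective size in Protocol 9.5), SE ≈ 1/√320 = 0.056. Points are bias × 16.6 to bias × 21.4, per SD of the covariate. The last column is the error rate of a nominal 5% test of a covariate with no association of its own: 1 − Φ(1.96 − bias/SE) + Φ(−1.96 − bias/SE).

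| b | r | Bias (SD) | Points | Bias/SE | Error rate |
|---|---|---|---|---|---|
| 0 | any | 0 | 0 | 0 | 5% |
| any | 0 | 0 | 0 | 0 | 5% |
| 0.1 | 0.1 | 0.01 | 0.17-0.21 | 0.18 | 5.4% |
| 0.1 | 0.3 | 0.03 | 0.50-0.64 | 0.54 | 8.4% |
| 0.2 | 0.3 | 0.06 | 1.00-1.28 | 1.07 | 18.9% |
| 0.3 | 0.5 | 0.15 | 2.49-3.21 | 2.68 | 76.5% |

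The SE is rough: it ignores the repeated visits, the centre effect, collinearity and the residual variance, which act in different directions. The SDs are for global satisfaction and come from other diseases, so the points speak at most to Table 19.

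**4. Age is a different case**

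Neither education nor disease duration can cause age. Leaving them out gives a total age association; adding them gives a direct one. SAP section 3 computes age at diagnosis as age minus COPD duration, so age and duration are tied by construction. Without duration in the model, the age coefficient does not separate being older from having had COPD longer.

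**5. Room in the model**

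Fixed-effect parameters now, counted without the intercept: age 1, gender 1, exacerbations 1, spirometry 1 to 6, mMRC or CAT 1, MMAS-4 1, visit 2; in total 8 to 13. Allowing 3 to 6 more for education, duration and a comorbidity term (an assumption, since the education categories are not visible) gives 11 to 19, or 320/19 = 17 to 320/11 = 29 patients per parameter.

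**The case against.** The strongest reply is that nothing in the documents shows any confounding. There is no reported association of education or duration with satisfaction in this population, or with exacerbations, symptoms or adherence. Protocol 9.13 promises adjustment only for what is in the model, and SAP 4.9 presents the analysis as exploratory. The section 7 text also names expectations, preferences and treatment characteristics, so any covariate list involves choice. Most of this stands: it limits the point to possible confounding and lowers its weight. It does not explain why two named variables, both already collected, are left out. Exploratory status does not remove bias either.

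A reader might infer more than the documents support:
- **That the coefficients are confounded as a matter of fact.** This needs a non-zero b and a non-zero r, and neither is documented.
- **That the age estimate is biased in the same sense.** It is a different quantity, total rather than direct, as step 4 shows.
- **That the error rates in step 3 predict how the models will perform.** They follow from assumed inputs and an approximate SE, and zero bias is within the range.
- **That comorbidity is a determinant named by the protocol.** It is not.
- **That the SAP departs from the protocol here.** It does not; Protocol 9.7 omits the same variables.

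Missing data is a fair worry for education, because SAP section 4 provides for values that are not known, not available or not recorded. It is not one for COPD duration: SAP 2.1 requires a diagnosis date for the full analysis set, and the models use a subset of that set.

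**Conclusion.** The point holds as an unexplained gap in covariate choice. Education and COPD duration are named as determinants, collected at enrolment and absent from all three models, so the coefficients for exacerbations, symptoms and adherence may be confounded by them. The age coefficient combines age's own association with those of education and duration. The size cannot be derived from the documents; the step 3 range of 0 to 0.15 SD is an illustration resting wholly on the assumed b and r. Because the analysis is secondary and exploratory, and the primary objective is a description of scores by visit that does not use these models, this is a worthwhile low-cost improvement and not a defect that undermines the study.

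**What to change.** - Add highest education level and COPD duration in years, as derived for Table 6, to the covariates of Tables 17-19, and exempt both from stepwise selection. Do not add age at diagnosis as well: it is an exact function of age and duration.
- Examine comorbidity in a sensitivity model using one measure for all patients, the count of ongoing comorbidities behind Table 7. A Charlson score for some patients and a count for others would mix two scales according to local coding practice.
- Report coefficients as associations conditional on the listed covariates, and drop the word *impact*.
- If the two variables are deliberately left out, state the reason in SAP 4.9.

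The cost is SAP wording, one derived count, a few more parameters, and the loss of patients with missing education unless it is imputed. No new data are needed. Both additions are enrolment variables, so they fit the sponsor's decision, recorded in SAP 4.9, to use baseline covariates only.

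### Objective #2 is framed around pre-defined variables, but SAP 4.9 drops non-significant interactions and leaves open stepwise selection, which overstates weak predictors if used

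*SAP*

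**What the plan says.** SAP section 4.9 opens with the aim of the objective #2 models: "The purpose of this secondary analysis is not to obtain a predictive model, but to investigate the relationship among pre-defined variables and outcomes". It adds that "the intent of this analysis is mainly exploratory and not confirmatory of any a priori hypotheses".

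Under Table 17 it lists the covariates, all taken at enrolment: age, gender, number of exacerbations, spirometry, mMRC or CAT, and MMAS-4. Centre is a random effect and visit is the timepoint. Two choices within the list are left to the analysis. For spirometry, "a selection of the following parameter will be done, based on data availability: FEV1, FVC, FEV1 % of the predicted, RV, TLC, DLCO". For mMRC and CAT, "only one of such measures will be considered in the model". Highly correlated variables, and those with much missing data, may also be removed.

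Two further rules follow. On interactions: "interaction terms between independent variables will be evaluated and, if not significant, they will not be included in the final model". On main effects: "A stepwise selection method will be evaluated during the analysis in order to identify the variables to be included in the final model". Tables 18 and 19 apply the same approach to the other two TSQM-9 domains.

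Protocol section 9.7 lists the covariates with no selection step. Protocol section 9.13 says that the models "will provide adjusted estimates of the impact on satisfaction scores of each variable keeping constant the others included in the models".

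**The concern.** Stepwise selection serves prediction, and section 4.9 disclaims prediction. When the question is how each of a short list of chosen variables relates to satisfaction, a weak or absent relation is itself a result. Letting significance decide what stays removes those results and distorts the survivors: a weak predictor is kept mainly in samples where its estimate happens to be large. The usual confidence interval is then computed as if the model had been fixed beforehand.

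The interaction rule raises a related problem. With no list, every pair is open to testing in each of three models, and the terms reported are those that passed.

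At stake is the reading of Tables 17 to 19: which factors appear related to satisfaction, and how strongly.

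**Working it through.** **The plan's own figure.** The only design calculation is Table 2 in protocol section 9.5: half-width = 1.96 × SD/√N. With SD 21.4 this gives 2.152 (N = 380) and 2.345 (N = 320). With SD 16.6 it gives 1.669 and 1.819. All four reproduce. They concern the mean global satisfaction score; nothing comparable is given for objective #2.

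**Inputs.** The effective sample size of 320 to 380 comes from protocol section 9.5. The covariate list comes from SAP section 4.9. The 0.05 level, the effect sizes and the use of one record per patient are assumptions.

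**Selection effect for one predictor.** Take z ~ N(μ, 1) with μ = r√n, kept when |z| > 1.96.
- Probability kept: K = Φ(μ − 1.96) + Φ(−μ − 1.96).
- Mean when kept: μ + [φ(1.96 − μ) − φ(1.96 + μ)]/K. Dividing by μ gives the overstatement.

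| Partial correlation r | μ (n = 320) | Kept | Overstated, n = 320 | Overstated, n = 380 |
|---|---|---|---|---|
| 0.05 | 0.894 | 14.5% | 2.69-fold | 2.50-fold |
| 0.10 | 1.789 | 43.2% | 1.51-fold | 1.41-fold |
| 0.20 | 3.578 | 94.7% | 1.03-fold | 1.02-fold |

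**Full stepwise, by simulation.** Assumptions: ordinary least squares, one record per patient, nine standardised candidates, residual SD 20, three true slopes plus six nulls, candidate correlation 0 or 0.3, entry and stay p of 0.05 or 0.15, N of 320 or 380, and 800 replicates per setting.

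| True slope (points per SD) | Mean when retained | Ratio | CI coverage when retained |
|---|---|---|---|
| 1.5 | 2.31 to 3.18 | 1.5 to 2.1 | 86 to 94% |
| 2.5 | 2.82 to 3.52 | 1.1 to 1.4 | 93 to 97% |
| 4.0 | 4.00 to 4.45 | 1.0 to 1.1 | 94 to 97% |

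- At least one null variable was retained in 27 to 31% of runs at p = 0.05, and in 62 to 64% at p = 0.15.
- The interval for a retained null covered zero in 0% of cases at p = 0.05 (by construction) and in 57 to 66% at p = 0.15.
- Stepwise standard errors were 0.91 to 0.99 of the full-model values.
- The full fixed model gave mean slopes of 1.43 to 1.57, 2.45 to 2.54 and 3.95 to 4.05, with coverage of 93 to 96%.

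**Interactions.** Age, gender, exacerbations, one of mMRC or CAT, and MMAS-4 make five covariates. One to six spirometry measures bring the total to 6 to 11.
- Pairs per domain: C(6,2) = 15 to C(11,2) = 55.
- Pairs over three domains: 45 to 165.
- Expected false positives at 0.05 if no interaction is real: 45 × 0.05 = 2.25 to 165 × 0.05 = 8.25.
- Chance of at least one per model, if tests are independent: 1 − 0.95^15 = 54% to 1 − 0.95^55 = 94%.

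**The case against.** The strongest reply is that section 4.9 says only that stepwise will be evaluated, within a secondary analysis declared exploratory. This stands in part. A reader might infer that Tables 17 to 19 will contain inflated coefficients. The documents do not support that: the consequence follows only if stepwise is adopted. What is established is that the selection rule is undecided. The interaction rule, by contrast, is firm. The exploratory label lowers what is claimed for the results, but it does not correct an estimate or interval obtained after selection.

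Other points on this side also stand:
- It would be wrong to infer that every retained coefficient is materially biased. In the simulation the strong predictor was inflated by 0 to 11% with near-nominal coverage.
- The planned model is a mixed model with up to three TSQM-9 records per patient, so the multipliers above do not carry over exactly.
- Dropping non-significant interactions does little to the main effects; the bias lies in the interactions that are kept.
- Choosing spirometry and mMRC or CAT by availability, and removing collinear variables, does not use the outcome and is not a source of this bias.
- The protocol 9.13 sentence can be read as covering only the variables in the fitted model. Set beside the fixed list in protocol section 9.7, however, the natural reading is that each listed variable gets an estimate.
- The table layouts are not shown in the public copy, so it cannot be said that full-model estimates would be absent from the report, only that section 4.9 does not commit to them.
- The three domains could end with different covariate sets, but neither document plans to compare coefficients across domains, so no stated aim fails on that account.

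**Conclusion.** The concern holds in conditional form. SAP section 4.9 states a purpose that calls for a fixed model. It then applies a significance rule to an open set of interactions and leaves stepwise selection of the final covariates to be decided during analysis.

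If stepwise is used, dropped variables lose their adjusted estimate, and retained weak or null predictors are overstated with unadjusted intervals. The illustrative size is about 2.7-fold at a partial correlation of 0.05, 1.5-fold at 0.10 and 1.03-fold at 0.20. These figures rest on an assumed 320 patients with one record each and selection at 0.05. The interaction rule could yield about 2.3 to 8.3 false positives over three domains, again at an assumed 0.05, the range reflecting 6 to 11 candidate covariates.

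The primary objective is unaffected. For a secondary, exploratory objective this is a change that should be made, because it costs little and removes an avoidable bias.

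**What to change.** In SAP section 4.9:

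1. Delete the stepwise sentence and the rule that drops interactions by significance.
2. Make the full listed main-effects model, with visit and random centre, the main result. Keep the outcome-blind choices based on availability and collinearity, and apply them identically in all three domains.
3. Report every coefficient with its 95% CI, whatever its p-value.
4. Name in advance any interaction of interest.
5. If a stepwise model is still wanted, label it supportive and state its entry and stay criteria.

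The cost is SAP wording only. The downside is slightly wider intervals from keeping weak covariates: in the simulation, stepwise standard errors were at most about 9% smaller than those of the full model.
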